6.3 Study Size

There will be 40 zirconia crowns and 40 ceramic onlays placed. The sample size is according to the international standard represented by the criteria of the American Dental Association (ADA, Council on Scientific Affairs: Acceptance Program Guidelines "Restorative Materials", March 1996). 60 patients will be enrolled in the study.

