There will be two datasets analyzed at each recall period; (1) one dataset consisting of subjects who were enrolled up to and including that recall period, and (2) one dataset consisting of all subjects with baseline data. In the second dataset (2) primary and secondary outcome variables which are missing will be imputed using the method of last observation carried forward (LOCF), wherein the last observed values for that variable will be carried forward to all remaining timepoints.

The primary analysis for this study will be the percent of intact/surviving restorations from baseline to the end of each recall period. This will be estimated using the Kaplan-Meier method, there will be no direct comparisons within this analysis. The median survival time of a restoration will be presented alongside survival curves.

The secondary analyses for this study will relate to the FDI criteria for esthetic properties including surface luster, surface staining, margin staining, color match and translucency; functional properties including anatomical form, material fracture, retention,

margin adaptation, occlusal contour and wear, and proximal contact and contour; and biological properties including post-operative sensitivity, caries, gingival index, and plaque index (see Appendix for FDI criteria description). The FDI criteria will be assessed at each recall period versus their respective baseline scores for a particular restoration within a particular subject. FDI criteria which are measured in an ordinal-discrete manner will be assessed using the Wilcoxon-signed rank test. Criteria which are measured continuously such as PI and GI will be assessed using the student's t-test, in the event that the PI and GI scores do not appear to be Normally distributed this assessment will shift to be done using the Wilcoxon-signed rank test.

A two-sided alpha of 0.05 will be used for all comparisons. There will be no adjustments made for multiplicity.

All statistical analyses will be performed e.g. using SAS version 9.4 or above (SAS Institute, Cary, NC).

9 Project Time Line

The recruitment of patients and clinical placement of restorations will begin immediately upon approval and funding of the project. It is anticipated to take 9-12 months to recruit and place the restorations required for the study.

Protocol Amendments and Discontinuing the Study

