 Esthetics	 Fractured restoration
 Fracture lines	 Open margins
 Severe wear	 Cervical overhang
 Poor contour	 Open proximal contact
4. Pre-operative shade: _____
5. Opposing restorative material: _____
6. Evidence of wear facets on the test tooth: Yes No
7. Evidence of lateral interference(s) on test tooth: Yes No

Comments

FDI CLINICAL EVALUATION CRITERIA

Gingival Index

Gingival score (visual) for gingival area nearest to the restoration margin; evaluate without disclosing.

(Gingival scores will be based upon the standard Loe & Silness Index, 1963)

score 0 = normal gingiva

score 1 = mild inflammation - slight change in color, slight edema, no bleeding

score 2 = moderate inflammation - redness, edema and glazing, bleeding on probing

score 3 = severe inflammation - marked redness and edema, ulceration, spontaneous bleeding

Plaque Index

Plaque score (visual) for facial gingival area nearest to the restoration margin; evaluate without disclosing.

(Plaque scores will be based upon the standard Silness & Loe Index, 1964)

score 0 = no plaque detectable in the gingival area

score 1 = plaque recognized only by running tip of probe across tooth surface at gingival crest

score 2 = moderate accumulation of plaque visible along gingival margin and adjacent tooth

score 3 = abundance of plaque visible along gingival margin and adjacent tooth

A. Aesthetic properties	1. Surface lustre	2a. Surface Staining	2b. Margin Staining
1. Clinically excellent / very good	1.1 Lustre comparable to enamel, Smooth, high gloss surface	2a.1 No surface stain	2b.1 No margin stain
2. Clinically good (after polishing probably very good)	1.2.1 Slightly dull, not noticeable from speaking distance. 1.2.2 Some isolated pores.	2a.2 Minor surface staining, easily removable by gentle polishing (prophy cup)	2b.2 Minor marginal staining, easily removable by gentle polishing (prophy cup)

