3. Clinically sufficient / satisfactory (minor shortcomings, no unacceptable effects but not adjustable w/o damage to the tooth)	1.3.1 Dull surface but acceptable if covered with film of saliva. 1.3.2 Multiple pores on more than one third of the surface.	2a.3 Moderate surface staining that may also present on other teeth, not aesthetically unacceptable.	2b.3 Moderate marginal staining, not aesthetically unacceptable.(aggressive removal of surface)
4. Clinically unsatisfactory (but repairable)	1.4.1 Rough or pitted surface, cannot be masked by saliva film, simple polishing is not sufficient. Further intervention necessary. 1.4.2 Voids.	2a.4 Surface stain not removed by gentle polishing, penetrates crown surface, major intervention necessary for improvement. (aggressive removal of material + adding material)	2b.4 Pronounced margin staining, Deeper penetration of the margin, major intervention necessary for improvement. (aggressive removal of material + adding material)
5. Clinically poor (replacement necessary)	1.5 Very rough, unacceptable plaque retentive surface.	2a.5 Severe Subsurface staining within the body of the crown, not accessible for intervention, removed only by replacement of crown	2b.5 Deep and widespread margin staining that penetrates margin, not accessible for intervention removed only by crown replacement

A. Aesthetic properties	3. Colour match and translucency	4. Aesthetic anatomical form
1. Clinically excellent / very good	3.1 Good colour match, no difference in shade and/or translucency.	4.1 Form– comparable to natural tooth anatomy.
2. Clinically good (after polishing probably very good)	3.2 Minor deviations in shade and/or translucency	4.2 Form is only slightly deviated from natural tooth anatomy.
3. Clinically sufficient / satisfactory (minor shortcomings, no unacceptable effects but not adjustable w/o damage to the tooth)	3.3 Distinct deviation but acceptable. Does not affect aesthetics: 3.3.1 more opaque 3.3.2 more translucent 3.3.3 darker 3.3.4 brighter	4.3 Form deviates from the natural anatomy but is aesthetically acceptable.
4. Clinically unsatisfactory (but repairable)	n.a.	4.4. Form is affected and unacceptable aesthetically. Intervention/correction is necessary.
5. Clinically poor (replacement necessary)	3.5 Unacceptable. Replacement necessary.	4.5 Form is unsatisfactory and/or lost. Repair not feasible / reasonable, replacement needed.

B. Functional properties	5a. Fracture of material	5b. Retention	6. Marginal adaptation

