1. Clinically excellent / very good	5a.1 No fractures / cracks	5b.1 Restoration in place	6.1 Harmonious outline, margins not detectable
2. Clinically good	5a.2 Small hairline crack.	n.a.	6.2 margins detectable: Slight ditching, slight step/flashes, minor irregularities.
3. Clinically sufficient / satisfactory (minor shortcomings, no unacceptable effects but not adjustable w/o damage)	5a.3 Two or more or larger hairline cracks and/or material chip fracture not affecting the marginal integrity or approximal contact.	n.a.	6.3 moderate detectability: Major irregularities, ditching or flash, steps or minor crevice formation
4. Clinically unsatisfactory / (but repairable)	5a.4.1 Material chip fractures which damage marginal quality or approximal contacts	n.a.	6.4.1 major crevice formation 6.4.2 Larger irregularities or steps (repair necessary)
5. Clinically poor (replacement necessary)	5a.5multiple fractures	5b.5 Complete Loss of restoration	6.5 Generalized major gaps/crevice formation or irregularities.

B. Functional properties	7. Occlusal contour and wear	8. Approximal anatomical form a. contact point b. contour
1. Clinically excellent / very good	7.1 No evidence of occlusal wear, wear equivalent to enamel	8a.1 Normal contact point (floss or 25 µm metal blade can pass) 8b.1 Normal contour.
2. Clinically good	7.2 Evidence of local facet formation < 2.0 mm in diameter, no change in occlusal anatomy, wear only slightly different from that to enamel	8a.2. Contact slightly too strong but no disadvantage (floss or 25 µm metal blade can only pass with pressure). 8b.2 Slightly deficient contour.
3. Clinically sufficient / satisfactory (minor shortcomings, no unacceptable effects but not adjustable w/o damage)	7.3 Evidence of local facet formation > 2.0 mm in diameter, slight change in occlusal anatomy, Different wear rate compared to enamel	8a.3. Somewhat weak contact, no indication of damage to tooth, gingiva or periodontal structures; 50 µm metal blade can pass 8b.3 Visible deficient contour
4. Clinically unsatisfactory / (but repairable)	7.4 Evidence of generalized facet formation with evidence of generalized wear altering occlusal anatomic form, Wear considerably exceeds normal enamel wear	8a.4 Too weak and possible damage due to food impaction; 100 µm metal blade can pass 8b.4 Inadequate contour Repair possible.

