4. Clinically unsatisfactory (repair for prophylactic reasons)	11.4.1 Intense hypersensitivity. 11.4.2 Delayed with minor subjective symptoms. 11.4.3 No clinical detectable sensitivity. Intervention necessary but not replacement.	12. 4.1 Caries with cavitation and suspected undermining caries 12.4.2 Erosion in dentin 12.4.3 Abrasion/ abfraction in dentin. Localized and accessible can be repaired.
5. Clinically poor (replacement necessary)	11.5 Intense, acute pulpitis or non-vital tooth. Endodontic treatment is necessary, and restoration has to be replaced.	12.5 Deep caries or exposed dentine that is not accessible for repair of restoration.

3M
Health Care
EM-11-CR 19-03
University of Michigan School of Dentistry

**Adverse Event
Record**

AE# Site Number

Subject Number

Date of onset:
Year Month Day

NOTICE: Contact 3M Study Monitor ASAP if the adverse event is serious or unanticipated/unexpected.

Specify the sign or symptom of the adverse event.

Identify study material(s) used at the site of the adverse event. (check all that apply)

 Suglue-3	 ADH-19	 Scotchbond Universal Etchant	 Chairside Zirconia
 CoJet Sand	 Vitrebond Plus Light cure glass ionomer liner/base	 Epilar Deep Cure S	

Other: _____

*Severity at Onset (Check one)	Seriousness (Check one)	Anticipated / Expected (Check all that apply)	Related to Study Material (Check one)	Action Taken (Check all that apply)

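### The FDI analyses in Section 8 do not separate scores taken after a study restoration was repaired or polished, so a treated defect can be absent from later recalls

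*Combined protocol and SAP*

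**What the plan says.** Section 8 (Statistical Analysis) sets the secondary analysis: "The FDI criteria will be assessed at each recall period versus their respective baseline scores for a particular restoration within a particular subject". Ordinal criteria are tested with the Wilcoxon signed-rank test, separately for onlays and crowns. "A two-sided alpha of 0.05 will be used for all comparisons", without multiplicity adjustment. Two datasets are analysed at each recall. The only data-handling rule is last observation carried forward, and it applies to missing values.

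The FDI tables in the Appendix tie several grades to treatment:
- Margin staining, grade 2: "Minor marginal staining, easily removable by gentle polishing (prophy cup").
- Margin staining, grade 4: "Deeper penetration of the margin, major intervention necessary for improvement".
- Marginal adaptation, grade 4 (6.4.2): "Larger irregularities or steps (repair necessary").
- Caries, erosion and abfraction, grade 4 (12.4): "Localized and accessible can be repaired".

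Grade 5 is tied to replacement, not repair.

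Section 7.3, under Restoration Failures, lists loss or loosening, fracture or chipping, and surface roughening or discoloration as failures to be reported to the sponsor. Caries and marginal gaps are not on that list. The primary Kaplan-Meier analysis in Section 8 concerns intact or surviving restorations, but the plan does not say whether a repaired restoration is still intact.

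**The concern.** Aim 3 is longitudinal clinical performance over at least three and up to five years. Repair is a consequence of a defect, yet under a plain reading of Section 8 a successful repair improves the later score. A margin graded 12.4 for cavitated caries at year 1 and then repaired can be graded 12.1 at year 2. A margin graded 6.4 can likewise return to 6.1. The post-repair score is observed, not missing, so the carry-forward rule does not touch it and it enters both datasets unflagged.

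The trial makes no between-group comparison in which such an effect could cancel. A reader of the year-3 FDI table would therefore see the condition of restorations that may have been maintained, without knowing how many had needed it. An analyst given only the observed scores could not tell a treated criterion from one that improved for another reason.

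**Working it through.** **The plan's own figure.** Section 6.3: "There will be 40 zirconia crowns and 40 ceramic onlays placed". The basis is external: "The sample size is according to the international standard represented by the criteria of the American Dental Association". No power, effect size, event rate or dropout is given, so 40 cannot be re-derived. It serves here only as the denominator: 1/40 = 2.5 percentage points per restoration.

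**Assumptions (not in the documents).** All 40 restorations of one type start at grade 1 on a criterion and all are seen at the later recall. At an earlier recall, k are at grade 4. Before the later recall, m of these are repaired, and the rest stay at grade 4. No other score changes. I took k from 4 to 10.

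**Formulas.**
- Grade-4 share at the later recall = (k − m)/40.
- Share ever at grade 4 = k/40.
- Mean grade, if repair returns the score to grade 1 = 1 + 3(k − m)/40.
- Signed-rank test: zero differences drop out. With r non-zero differences, all in the same direction, the exact two-sided p is 2 × 0.5^r (1.0 if r = 0).

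**Repair back to grade 1, so r = k − m.**

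| k | m | grade 4 at later recall | ever grade 4 | mean grade | exact p |
|---|---|---|---|---|---|
| 4 | 0 | 10.0% | 10.0% | 1.300 | 0.125 |
| 4 | 4 | 0% | 10.0% | 1.000 | 1.0 |
| 6 | 0 | 15.0% | 15.0% | 1.450 | 0.031 |
| 6 | 1 | 12.5% | 15.0% | 1.375 | 0.0625 |
| 6 | 3 | 7.5% | 15.0% | 1.225 | 0.25 |
| 6 | 6 | 0% | 15.0% | 1.000 | 1.0 |
| 8 | 0 | 20.0% | 20.0% | 1.600 | 0.0078 |
| 8 | 3 | 12.5% | 20.0% | 1.375 | 0.0625 |
| 10 | 0 | 25.0% | 25.0% | 1.750 | 0.0020 |
| 10 | 5 | 12.5% | 25.0% | 1.375 | 0.0625 |

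For k = 6 the step is 2 × 0.5^6 = 0.031 to 2 × 0.5^5 = 0.0625. One repair crosses the 0.05 threshold. For k = 8 it takes three, and for k = 10 it takes five.

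**Repair to grade 2.** Every treated restoration is still one grade worse than baseline, so r = k and p does not move: 0.031 for k = 6 and 0.0078 for k = 8. Only the distribution improves. With all 6 repaired to grade 2, the mean is 1 + 6/40 = 1.15 instead of 1.45, and no restoration is at grade 4.

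**Polishing at grade 2.** A restoration at grade 1 at baseline, grade 2 at one recall and polished back to grade 1 has a zero difference at the next recall and drops out of that test.

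**The case against.** A reader might infer that the plan directs repaired restorations to be scored as though nothing had been done. It does not. Section 8 is silent, and the effect follows only from applying its comparison literally. Nor does any section schedule repair followed by continued scoring. That sequence is inferred from the scale's descriptors, while the resolutions described under Restoration Failures and in Section 12 are replacement or alternative treatment.

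A reader might also infer that the defect leaves the trial's results altogether. It does not. Analyses are run at each recall, so a grade 4 at year 1 stays in the year-1 results. Chipping, roughening and discoloration are on the failure list and may count as events in the Kaplan-Meier analysis. Treatment that was unplanned may be recorded on the adverse event form. These points stand. They make caries and marginal adaptation the clearest cases, since neither is on the failure list. They do not close the gap: nothing links that list to Section 8, and the adverse event form has no field for FDI criterion or pre-treatment grade.

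Observed status at each recall is also a legitimate target. It is a prevalence, and the proportion ever affected is a different quantity that Section 8 does not claim to report. Making the worst grade the main analysis would hold a polished grade 2 stain against a restoration for years. This is a good reason to keep the observed-score analysis and add to it.

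Finally, the recall form is not among the forms in the Appendix, so it may already have an intervention item. The missing analysis rule does not depend on that.

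**Conclusion.** The point holds as a gap in the secondary FDI analyses and in the definition of intact status. Scores taken before and after treatment are not distinguished, so later-recall results can describe the restoration plus its repairs. The documents give no repair rate, so the size is known only per restoration (2.5 points of 40) and by illustration: 10% can become 0% with 4 repairs, and one repair among 6 affected moves p from 0.031 to 0.0625. The effect on the test needs the score to return to its baseline value. Short of that, only the grade distribution changes.

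It would be too strong to say that the bias is always favourable or must grow with follow-up. It depends on how many restorations are treated and to what grade, and nothing in the documents rules out polishing or adjustment worsening another criterion. Generally favourable is as far as the text supports. The analyses concerned are secondary, within-group and unadjusted. The change is worth making because it is cheap and the information is hard to recover afterwards.

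**What to change.** 1. At each recall, record any intervention on the study restoration since the last visit or at this one: type, date, criterion affected and pre-intervention grade. Score before any polishing at that visit. If the recall form already has these items, refer to them in Section 8.
2. Keep the observed-score comparison with baseline in Section 8. Add, per criterion and restoration type, the cumulative proportion of restorations ever at grade 4 or 5.
3. Add a sensitivity analysis that uses the worst grade to date for treated criteria.
4. State whether a repaired restoration still counts as intact in the Kaplan-Meier analysis, and reconcile that definition with the list under Restoration Failures in Section 7.3. The sponsor and investigator must settle which reading applies.

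The cost is one more form item, one more table and a few sentences in Section 8, with no extra visits. Late-recall FDI results may look slightly less favourable.

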6.1 Subjects

The patient population will be selected from current patients under clinical treatment at the University of Michigan Dental Clinics. Patients need to volunteer for the study and must sign the informed consent. Patients will be over 18 years of age, of either gender, and of any ethnic background. Each patient should have at least one carious lesion or defective restoration to be restored on a maxillary or mandibular premolar or molar. Each lesion or defective restoration should exhibit sufficient size to extend at least one-half the intercuspal width of the tooth requiring an onlay or full crown restoration. The onlays may contain between one and three cusps on the selected tooth as long as an occlusal margin will be present. All teeth will test vital and be asymptomatic at the beginning of treatment. No more than two restorations will be placed per patient. If a patient presents with more than two acceptable teeth for the study, molar teeth will be included prior to premolar teeth. Exclusion criteria will include:

Devital or sensitive teeth

Teeth diagnosed with symptoms of incomplete tooth fracture

Teeth with prior endodontic treatment of any kind

Teeth with a history of direct or indirect pulp capping procedures

Subjects with uncontrolled bruxism or parafunctional habits

Subject has known allergies to any product used during this study

Subject will not be available for the study duration of 5 years

Subjects with significant untreated dental disease to include periodontitis and rampant caries

Pregnant or lactating women

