Furthermore he/she will check the availability, completeness, logicalness, accuracy and legibility of certain study documents, the CRFs and the Adverse Event/Incident forms. The occurrence of any new Adverse Event/Adverse Device Effect/(near) incident will be reported in the monitoring report and copies of the forms will be collected. Certain data in the CRFs will be verified with source documents (patient files).

The study will be monitored at appropriate intervals by the study monitor, or his/her designee, by means of visits to the study site to evaluate study data and any photographs. Study monitoring visits will involve review of the study status and any issues pertaining to it. All Informed Consent forms, HIPAA forms will be reviewed for signatures; all CRF's will be reviewed for completeness of data entry and that the study protocol is being followed; the subjects'

profiles will be checked to ensure they meet the inclusion and exclusion criteria. Materials will be checked for adequate storage and sufficient quantity to meet the study needs.

Data collection and Data corrections

During monitoring, CRFs will be checked for accuracy, legibility, logicalness and completeness, that all patients have given informed consent, meet selection criteria, and have had treatments randomly allocate in accordance with the study protocol. Resulting changes in the data will be initialized and dated by the person who changed them. If all open questions could be cleared with the investigator, copies of the signed Adverse Event/Incident forms will be provided for the Study Monitor's file. Data entry will be done by [REDACTED], Research Clinic Coordinator of the Cariology, Restorative Sciences Clinical Research Unit.

8 Statistical Analysis

In general, all analyses will be conducted separately by type of restoration; onlay or crown. Means and standard deviations were calculated for all clinical measurements and assessments. Categorical variables were summarized in frequency distributions.

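### At least 20 of 60 patients carry two restorations, but Section 8 tests restorations of one type as independent, so secondary p-values (chiefly gingival and plaque index) can be slightly too small

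*Combined protocol and SAP*

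**What the plan says.** Section 6.3 plans 40 zirconia crowns and 40 ceramic onlays in 60 patients. Section 6.1 sets the cap: "No more than two restorations will be placed per patient". Its only selection rule among eligible teeth is by tooth position: "If a patient presents with more than two acceptable teeth for the study, molar teeth will be included prior to premolar teeth". The enrollment form in the Appendix admits a subject who needs a crown, an onlay or both.

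Section 8 then fixes the analysis:

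- **Strata:** "In general, all analyses will be conducted separately by type of restoration; onlay or crown".
- **Unit of the secondary comparisons:** "The FDI criteria will be assessed at each recall period versus their respective baseline scores for a particular restoration within a particular subject".
- **Ordinal criteria:** "FDI criteria which are measured in an ordinal-discrete manner will be assessed using the Wilcoxon-signed rank test".
- **GI and PI:** "Criteria which are measured continuously such as PI and GI will be assessed using the" Student t-test, and if the scores do not look Normal "this assessment will shift to be done using the Wilcoxon-signed rank test".
- **Level:** "A two-sided alpha of 0.05 will be used for all comparisons", with no multiplicity adjustment.

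The primary analysis is a Kaplan-Meier estimate with no comparison.

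**The concern.** The signed-rank test and the t-test on changes both assume that the changes are independent. Two crowns, or two onlays, in one mouth need not change independently. The wording in Section 8 about a restoration within a subject defines the pairing of recall with baseline. It does not deal with two restorations of the same type in one patient.

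The mechanism is narrow. A stable patient effect, such as generally poor hygiene, cancels when baseline is subtracted. What remains is change between visits that is shared within the mouth. That is most plausible for GI and PI, which the Appendix scores 0 to 3 at the gingival area nearest the restoration margin. Criteria that can only worsen from baseline are outside this point. Retention, which the Appendix scores only 1 or 5, is an example.

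At stake is the true error rate of the secondary tests. No success rule depends on them, and the Kaplan-Meier estimate and median are unaffected.

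**Working it through.** **Count.** Inputs: 40 + 40 = 80 restorations and 60 patients (Section 6.3), at most 2 per patient (Section 6.1). Patients with two = 80 − patients restored ≥ 80 − 60 = 20. It is exactly 20 if all 60 receive a restoration, and more if some receive none.

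**Which pairs matter.** Analyses are separate by type, so only same-type pairs count. The plan does not give their number. If types fell at random over 20 pairs, each type would expect 20 × (40/80) × (39/79) = 4.9 pairs. I use 5 as a central case, 10 per type (all 20 pairs same-type, split evenly) as a high case, and 20 in one type as the extreme.

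**Formula.** With k same-type pairs among n = 40 and correlation ρ between the *changes*, the design effect is DE = 1 + 2kρ/n. The actual two-sided level is 2[1 − Φ(1.96/√DE)]. With ρ = 0 or k = 0 this returns the plan's 0.05.

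| Pairs k | DE at ρ = 0.1 / 0.3 / 0.5 | Level at ρ = 0.1 / 0.3 / 0.5 |
|---|---|---|
| 5 | 1.025 / 1.075 / 1.125 | 0.053 / 0.059 / 0.065 |
| 10 | 1.05 / 1.15 / 1.25 | 0.056 / 0.068 / 0.080 |
| 20 | 1.10 / 1.30 / 1.50 | 0.062 / 0.086 / 0.110 |

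**Simulation on scores like GI and PI.** Scores 0–3 were drawn at baseline and recall. Half of the latent variance was stable per restoration, and visit effects were shared within patient at the stated ICC. Each case had 200,000 replicates. Two assumed score distributions (50/30/15/5% and 30/40/25/5%) give the ranges. The t-test is taken as the test on changes from baseline.

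| Pairs | Test | ICC 0.1 | ICC 0.3 | ICC 0.5 |
|---|---|---|---|---|
| 5 | signed-rank | 0.050–0.053 | 0.055 | 0.059–0.060 |
| 5 | t-test | 0.051–0.053 | 0.056 | 0.060–0.061 |
| 10 | signed-rank | 0.052–0.054 | 0.060–0.062 | 0.069–0.071 |
| 10 | t-test | 0.053–0.055 | 0.061–0.063 | 0.070–0.072 |
| 20 | signed-rank | 0.057–0.058 | 0.072–0.075 | 0.090–0.094 |
| 20 | t-test | 0.058–0.059 | 0.073–0.077 | 0.091–0.095 |

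With no pairs the levels are 0.048–0.049 (signed-rank) and 0.049–0.051 (t-test).

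A generic five-level change (−2 to 2 with probabilities 5/15/60/15/5%) gives similar signed-rank levels. At ICC 0.1 / 0.3 / 0.5 they are 0.050 / 0.055 / 0.061 (5 pairs), 0.052 / 0.062 / 0.073 (10 pairs) and 0.057 / 0.077 / 0.098 (20 pairs).

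**Why the two tables differ.** In the simulation the ICC is set on the latent scale. The realised correlation of the score changes is lower: 0.06–0.08, 0.21–0.26 and 0.35–0.43 for ICC 0.1, 0.3 and 0.5. Putting 0.35 and 0.43 into the formula with 10 pairs gives DE = 1.175 and 1.215, hence levels of 0.071 and 0.075. That is in line with the simulated t-test values of 0.070–0.072 (GI/PI model) and 0.076 (five-level model).

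**Practical size.** GI and PI at the four required recalls (6 months, 1, 2 and 3 years) for two types give 2 × 4 × 2 = 16 tests per dataset. If every null holds, expected false positives are:

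- as planned: 16 × 0.050 = 0.8
- 5 pairs per type at ICC 0.3: 16 × 0.055 = 0.88
- 10 pairs per type at ICC 0.5: 16 × 0.071 = 1.14

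**The case against.** The harm rests on facts that cannot be seen. If every two-restoration patient receives one crown and one onlay, there is no effect. Section 6.4 has a heading but no text in the copy read, so a pairing rule could stand there. The monitoring text in Section 7.3 also mentions random allocation of treatments, a procedure that the visible plan does not describe. This stands as a limit on certainty. Neither point shows that same-type pairs are barred, and the visible rules allow them.

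The central effect is small. A level of about 0.055 moves expected false positives from 0.8 to 0.9 over 16 tests. Testing without multiplicity adjustment matters far more: for 16 independent tests, 1 − 0.95^16 = 0.56 is the chance of at least one false positive. This also stands, and it is why the point is minor.

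The five-level model lets as many restorations improve as worsen. New restorations would be expected to start near the best score on most FDI criteria, so the model fits few of them. This is fair, and the conclusion therefore leans on GI and PI. The documents give no correlation to prove that these two are the most affected; that is a clinical inference.

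Finally, an analysis with one restoration per patient per type might be enough for secondary outcomes. It would be valid, but it discards data that a clustered test keeps.

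**Conclusion.** The point holds and is minor. The count of at least 20 two-restoration patients is exact, and Section 8 makes no allowance for same-type pairs. How far the level rises depends on two assumed quantities: the number of same-type pairs and the correlation of their changes. For GI and PI the signed-rank level is about 0.055 with 5 pairs at a latent ICC of 0.3, and about 0.07 with 10 pairs at 0.5. It approaches 0.09 only if 20 pairs fall in one type at 0.5. If the correlation is set on the changes themselves, the last two become 0.080 and 0.110. With no same-type pairs the level stays at 0.05. Confidence is medium, because neither input is in the documents.

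**What to change.** In Section 8:

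1. State that the restoration is the unit and the patient is the cluster, and say whether a patient may receive two restorations of the same type.
2. For FDI, GI and PI changes, replace the ordinary signed-rank test with a patient-clustered one. Sum the signed ranks within patient to Sᵢ and refer ΣSᵢ / √(ΣSᵢ²) to the Normal distribution.
3. Where the t-test on GI or PI is kept, use a patient-clustered variance with factor G/(G−1) and a t reference on G−1 degrees of freedom, where G is the number of patients.
4. Report the number of patients and same-type pairs beside the number of restorations at each recall.
5. If a survival interval is reported (the plan names none), use a patient-clustered variance or a patient-level bootstrap.

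Over all simulated cases the clustered signed-rank test held the level at 0.046–0.050 and the corrected clustered t-test at 0.049–0.053. A plain robust standard error or GEE with a 1.96 cut-off should be avoided: it gave 0.060–0.073, and 0.060–0.062 even with no pairs. A patient-level sign-flip test is valid but conservative with tied scores (0.032–0.041) and costs some power.

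The cost is SAP wording and a few lines of code, with no extra patients, visits or data. P-values become slightly larger when positively correlated same-type pairs exist. With none, the clustered signed-rank test equals the ordinary normal-approximation test and the corrected clustered t-test equals the ordinary t-test.
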